****TAY Exiting the Adult Criminal System (ADULT POPULATION)****

Study population:

Participants who are eligible for the Whole Person Care—Los Angeles (WPC-LA) Reentry post-release program will be eligible for the adult population of this study. The WPC Reentry program, implemented by the Los Angeles County Health Services Department, links jail inmates with community-based health, behavioral health, and social service providers as they return to the community. The intervention connects participants to Community Health Workers (CHWs) with a prior personal history of incarceration. CHWs assist participants in engaging with community-based health, behavioral health, and social service providers during reentry to the community. Services provided include mentorship and social support; health and social service navigation; linkage to housing, employment, education, legal assistance and social supports; accompaniment to key health and behavioral health appointments; assistance with adherence to appointments, treatments and medications; and connection to transportation. The mentorship and social support aspects of the intervention will indirectly target the social networks of participants. The WPC intervention is an existing intervention. The WPC intervention enrolls 750 individuals per month across LA County; approximately 12% are transition age youth ages 18-24. Participants are invited to this program while detained by the WPC case manager. Thus, WPC is a voluntary program. The WPC case manager is responsible for determining eligibility for the WPC reentry program and enrollment in the WPC program, not the research staff.

Recruitment and Consent:

We will recruit 160 adults exiting the LA county justice system – 80 who have enrolled in the WPC program and 80 have not. We anticipate enrolling participants over an approximate 9 month window, aiming to recruit about 9 individuals per arm (WPC and non-WPC) each month. This represents approximately 10% of the eligible population each month for each arm.

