Following study subject involvement (completion of surveys), medical record abstraction will be completed in partnership with LA County. We anticipate that this will be completed via a systematic data pull that includes information for all study participants that have signed a HIPAA authorization form. Thus, no abstraction form is included. Chart data will include: arrests, time spent incarcerated, recidivism, health services utilization – such as hospitalization and treatment, health diagnoses, as well as uptake / utilization of the WPC program. This information, in conjunction with data collected via survey administration, will be used both as covariates to help control for any difference between the intervention and control groups as well as for outcomes data related to behavioral health uptake and recidivism.

Amendment 5/27/20:

Qualitative Interviews and Follow-up Survey

Due to COVID-19 pandemic, we are suspending all in-person procedures until allowed to resume. During this time, we will be conducting up to 9 monthly qualitative interviews over the phone with the 19 participants who are currently enrolled in the study; we have also added another time point for when the follow-up survey will be administered: 1 month after release. We have created an addendum consent and those participants that are currently enrolled will be asked, over the phone or in-person when permissible, whether or not they are interested in participating in the new study procedures. If they are interested, the RA will obtain verbal consent. Participants will receive \$25 for each of the qualitative interviews completed. They will also receive \$50 for completing the additional follow-up survey.

Amendment 10/28/20:

Recruitment and Consent:

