## **STATISTICAL DESIGN AND POWER**

### **Analytic Strategy**

For each of the aims, we will compare participants who received WPC pre-release services (control group) to participants who received WPC pre-release and post-release services (intervention group). To address possible differential uptake or attrition, we will also conduct treatment received analyses, using the percent time young people participated in the post-release program (9 months total for the initial cohort and 6 months total for the final cohort) as the predictor of outcome. We will also examine for balance on sociodemographic variables and other characteristics of interest between the intervention and control groups as a means of examining for selection bias. To address missing data, in the main analysis, we will use generalized mixed effects model for repeated measures, under the missing-at-random assumption. In addition, using multiple imputations with pattern-mixture models, we will conduct sensitivity analyses to investigate whether our findings are robust to the missing mechanisms (i.e., assuming missing-not-at-random). In particular, we will consider a scenario which is least favorable to the intervention arms; that is, a scenario where the missing observations in the intervention arm follow the same pattern as the one in the control arm.

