#### **Aim 1: Measure the impact of the WPC Reentry intervention targeting recently incarcerated young people on decreasing rates of 30-day use and risky use of marijuana, alcohol, and other drug use.**

*Hypothesis 1:* Young people receiving the WPC intervention will have less substance use at follow-up (3 and 9 months for initial cohort, and 4 and 6 months for final cohort) compared to their in the control group.

For the main outcome, percentage of days used marijuana in the last 30 days, we will conduct a linear mixed effects regression model to account for repeated measurements within individual young people. We will perform unadjusted and adjusted comparisons, controlling for baseline demographic (race/ethnicity, age, parental SES) and substance use characteristics, as well as any variables found to be differential between the intervention and control groups. Similar analyses will be carried out to examine the impact of WPC on percentage days used alcohol and other drugs, and risky use of marijuana, alcohol, and other drugs. We will estimate the treatment effect on marijuana use with the adjustment of incarceration based on the principle stratification analysis.

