#### **Aim 2: Test whether the WPC Reentry intervention decreases recidivism, increases receipt of behavioral health services, improves mental health, and enhances school and work engagement (secondary outcomes).**

*Hypothesis 2:* Young people receiving the WPC intervention will have less recidivism and mental health symptoms, and higher rates of receipt of community behavioral health services and school and work engagement.

For each of the secondary outcomes, recidivism, mental health symptoms, receipt of behavioral health services, and school and work engagement, we will conduct generalized linear mixed effects regression models to account for repeated measurements within individual young people, while controlling for baseline demographic and substance use characteristics, as well as any variables found to be differential between the intervention and control groups. We will also evaluate whether there is effect modification by baseline mental health symptoms, using interaction terms with the exposure variable in the regression analysis.

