### **Sample Size Estimate**

We estimated power for a 2-arm pilot trial. We plan to recruit and consent 160 transition-age young people exiting jail. With a sample size of 160, we believe that our study will be adequately powered to detect a minimal detectable difference in the percentage of days used marijuana in the past 30 days of 17%, which is equivalent to a decrease of 5 days of marijuana use in a 30-day period. This difference is within the observed effect seen in a prior study of marijuana use among reentry young people, which found a range of intervention effects from 11% to 38%. This calculation assumes 10% attrition rate at 3 months, two-sided test with alpha 0.05, and 80% power.

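### Supplementary treatment-received analysis: if re-arrest cuts participation in the post-release program, recidivism lowers its own predictor and a program with no effect can look beneficial

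*SAP*

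**What the plan says.** For every aim, the SAP (Analytic Strategy) compares controls, who had pre-release services only, with "participants who received WPC pre-release and post-release services (intervention group". To deal with differential uptake or attrition it adds treatment-received analyses whose predictor is the "percent time young people participated in the post-release program (9 months total for the initial cohort and 6 months total for the final cohort". The statistical section states no lag, landmark or time-updated exposure, and no rule for participation after a re-arrest.

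The substance-use outcomes in SAP Aim 1 fall at "3 and 9 months for initial cohort, and 4 and 6 months for final cohort". Recidivism, a secondary outcome under SAP Aim 2, is analysed with "generalized linear mixed effects regression models to account for repeated measurements within individual young people".

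The protocol's account of the adult population places the work in the community: "CHWs assist participants in engaging with community-based health, behavioral health, and social service providers during reentry to the community". Neither document says what happens to participation when a youth is re-arrested.

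On data sources, the protocol first planned a record pull ("Chart data will include: arrests, time spent incarcerated, recidivism, health services utilization", plus use of WPC). Its 10/28/20 amendment dropped that pull.

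**The concern.** A predictor should precede the outcome it predicts. Two features of the stated exposure work against that.

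- **Time order.** A single whole-program percentage contains time after any outcome measured before the program ends.
- **Reverse causation for recidivism.** Only post-release participation counts. If a re-arrest ends or pauses it, youth who are re-arrested have lower percentages because they were re-arrested. This acts at the last visit as well as the early ones.

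The distortion favors the program. At stake is a participation gradient on recidivism that seems to support SAP Hypothesis 2 although WPC has no effect. Readers would turn to this analysis if uptake proved poor.

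**Working it through.** **Plan's own figure.** The only design figure is the 17% detectable difference in marijuana days (0.17 × 30 = 5.1 days). No SD is given, so it cannot be reproduced independently; it implies SD = 17 / [(1.960 + 0.842) × √(2/72)] = 36.4 points. The present point does not depend on it. Only the sample size is carried over: 160 × 0.90 = 144, or 72 per arm. The SAP says "This calculation assumes 10% attrition rate at 3 months"; using 10% throughout is an assumption.

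**1. Time order.** Share of the exposure window after the outcome: (9 − 3)/9 = 67% for the 3-month survey and (6 − 4)/6 = 33% for the 4-month survey.

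**2. Assumed re-arrest hazard.** The protocol's Background gives 75% re-arrested within 3 years, for adolescents. With a constant hazard, −ln(0.25)/36 = 0.0385 per month. Cumulative risk is 1 − exp(−0.0385 × 6) = 20.6% by 6 months and 1 − exp(−0.0385 × 9) = 29.3% by 9 months.

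**3. Null simulation.** WPC has no effect. Initial cohort: 10 WPC and 9 controls (the 19 enrolled in May 2020; the split is assumed). Final cohort: 62 and 63. Controls are set at 0% participation, and WPC youth leave for other reasons at 2, 8 or 15% per month. The outcome is any re-arrest since the last survey (0–3 and 3–9 months; 0–2, 2–4 and 4–6 months). The model is a random-intercept logistic regression on whole-program percent, adjusted for cohort and visit. There were 1,500 trials per setting, two-sided 5%, counting benefit only (nominal 2.5%).

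| Effect of re-arrest on participation | False benefit at 2 / 8 / 15% leaving | Median OR, 100% vs 0% |
|---|---|---|
| none | 2.0 / 2.3 / 1.8% | 1.0 |
| ends it a quarter of the time | 8.3 / 5.3 / 4.7% | 0.77–0.79 |
| pauses it about 1 month | 7.6 / 6.2 / 4.8% | 0.74–0.76 |
| ends it half the time | 20.1 / 15.5 / 10.4% | 0.58–0.62 |
| pauses it about 3 months | 22.2 / 14.9 / 10.5% | 0.58–0.59 |
| always ends it (extreme) | 76.3 / 56.1 / 37.2% | 0.32–0.35 |

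A repeat run gave 11–23% for the half case. The arm comparison stayed at 1.8–2.1%.

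**4. Sensitivity to the hazard** (8% leaving). At 0.0193 per month: quarter 2.5%, 1-month pause 3.8%, half 5.2%. At 0.077: 9.1%, 10.6% and 25.4%.

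**5. Counting participation only up to each survey.** This used a simpler single-time logistic model with 80 per group, 40% re-arrested by program end and controls at 0%. If every re-arrest ends participation, the 9-month outcome gives OR 0.28 with 80% false benefit and the 3-month outcome OR 0.31 with 60%. If half do, the 3-month outcome gives OR 0.60 with 10%. The bias remains because a re-arrest shortens participation in the interval where it is counted.

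**6. Exposure measured before the interval, among youth not yet re-arrested.** False benefit is 1.7–2.9% with intervals starting at 2 months (final cohort) and 3 months (initial cohort), and 2–3% with the earlier surveys added as boundaries.

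**7. Events lost to the first interval.** Expected first re-arrests: 125 × 0.206 + 19 × 0.293 ≈ 31.4.
- Starting at 2 weeks and 1 month loses 125 × 0.0191 + 19 × 0.0378 ≈ 3.1 (10%).
- Starting at 2 and 3 months loses 125 × 0.0741 + 19 × 0.1091 ≈ 11.3 (36%).

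Power, if participation halves the hazard, is about 17–32% with the earlier start and 10–20% with the later one.

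**The case against.** The strongest reply is that the premise is absent. No text says re-arrest interrupts participation, and without interruption there is no bias. WPC meets people in jail, so contact after re-arrest is conceivable. This stands, and the point is therefore conditional. Interruption is still plausible, because the exposure counts only post-release time and the work is community linkage.

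The parenthesis may only give program length. That would answer the time-order part, but step 5 shows that it does not answer the recidivism part.

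The sizes are fragile. The hazard is a background figure for adolescents applied to ages 18–24, and the SAP does not say that controls enter at 0%. That also stands. Restricting to the intervention group does not help: with full interruption the simpler model gives OR 0.065 or lower.

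A reader might infer more than the documents support:
- *That the trial's main recidivism result is biased in this way.* The group comparison does not use participation time.
- *That substance-use results share the bias.* Early 30-day outcomes would do so only if use drives leaving WPC, which neither document addresses.
- *That recidivism is undefined.* The SAP text available starts at the statistical section, so this cannot be judged.
- *That new survey items are required.* The instrument is not in the documents, and the protocol's fidelity form already covers frequency and duration of coach contact.
- *That adjusting for incarceration only in the marijuana analysis shows a gap here.* For this analysis recidivism is the outcome itself.

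**Conclusion.** The point holds as a conditional one. As written, the exposure includes time after the 3- and 4-month outcomes. If re-arrest ends or pauses participation, the recidivism analysis leans toward benefit. Under the assumed hazard, 72 per arm and controls at 0%, false benefit rises from about 2% to 5–8% when a quarter of re-arrests end participation and to 10–23% when half do. At half the hazard the milder cases are close to the nominal 2.5%. Confounding of participation by need or motivation could add to this lean or offset it. Only a supplementary analysis of a secondary outcome in a pilot is affected, so the change is worth considering rather than essential.

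**What to change.** In the SAP's Analytic Strategy:

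- **Recidivism.** Define the exposure as percent of time in the post-release program from release to the start of each outcome interval. Model first re-arrest in that interval among youth not yet re-arrested or returned to custody, adjusted for cohort and interval.
- **Boundaries.** Use every scheduled survey: 2 weeks and 2, 4 and 6 months in the final cohort; 1 month (where completed), 3 and 9 months in the initial cohort. Some of the 19 may have been past 1 month when that survey was added.
- **30-day outcomes.** Count participation only up to the start of the 30-day window. This rule does not suit the 12-month risky-use index in the protocol, whose look-back reaches before release at every survey.
- **Reporting.** Name the source of participation data and label the result associational. If the surveys cannot place a re-arrest in an interval, leave recidivism out of this analysis.

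Removing custody time from the denominator is not a substitute. With a 1-month custody and half of re-arrests ending participation, false benefit is still 12.3 / 7.8 / 5.3% at the three leaving rates.

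**Cost.** SAP wording, and confirmation that the surveys (for example the fidelity form) date participation and re-arrest, since the record pull was dropped. The question changes from repeated recidivism to first re-arrest. About 10% of first re-arrests are lost under the assumed hazard, or up to 36% if the 2-week and 1-month surveys are not used. With power of about 17–32% at a hazard ratio of 0.5, the result is descriptive.

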Potential subjects will be identified as follows: (1) The research associate (RA) will shadow the WPC case manager as she invites participants to enroll in WPC. (2) The RA will then approach and ask potential WPC participants if they are interested in participating in the study, regardless of whether they accept to enroll in the WPC program or not. If the participant opts in to the WPC intervention, he/she will be placed in the “intervention” group of the study; if the participant opts out of the WPC intervention, he/she will be placed in the “non-intervention” group of the study. (3) If the participant is interested in participating in the study, the RA will confirm the age of the participant (must be between the ages of 18-24) and assess whether there are no severe cognitive delays based on communication with the participant.

If eligible, the RA will review the study with the interested participant and obtain written consent. Furthermore, the RA will obtain a signed HIPAA authorization form for research for medical record access to allow for later record review and abstraction. The RA will remind the participant of the voluntary nature of the study and that participation in no way affects their standing with the Court, the Sheriff’s department, or their receipt of WPC.

Data Collection:

The RA will administer the baseline survey in a private area where respondents’ answers cannot be overheard. Surveys have been piloted with TAY not in jail and take an average of 20 minutes to complete. Upon completion of the survey, the RA will ask for a telephone number and address to contact the participant after their release from incarceration. This information will be kept separate from the survey. To encourage follow-up, a \$50 cash or gift card incentive (based on participant’s preference) will be given to participants if they contact the research team after their release. At this time, participants will also be provided with a copy of the consent and HIPAA authorization forms.

Follow-up surveys will be conducted at 3 and 9 months post-release. These surveys will be conducted in-person or over the phone, based on participant’s preference, and are expected to last up to 30-minutes each. A \$50 gift card or cash incentive will be given after the completion of each follow-up survey.

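### Arm is the participant's own choice, yet selection bias is examined only through balance on measured characteristics, and no planned analysis bounds unmeasured confounding

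*SAP*

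**What the plan says.** **How arm arises.** The protocol (adult population, Study population) states: "Thus, WPC is a voluntary program". Under Recruitment and Consent it assigns groups by that choice: "If the participant opts in to the WPC intervention, he/she will be placed in the" intervention group, and "if the participant opts out of the WPC intervention, he/she will be placed in the" non-intervention group. The remote-recruitment text of the 10/28/20 amendment gives no other allocation rule. The SAP (Analytic Strategy) defines the arms by services received: "we will compare participants who received WPC pre-release services (control group) to participants who received WPC pre-release and post-release services (intervention group".

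**How selection is examined.** The same SAP section says "We will also examine for balance on sociodemographic variables and other characteristics of interest", and continues "between the intervention and control groups as a means of examining for selection bias".

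**How selection is handled.** For Aim 1 the SAP adjusts for demographics and baseline substance use, "as well as any variables found to be differential between the intervention and control groups". Aim 2 follows the same pattern. Aim 3 adds baseline network measures if they differ significantly.

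**What is claimed.** Aim 1 is to "Measure the impact of the WPC Reentry intervention targeting recently incarcerated young people". Aim 2 tests whether WPC lowers recidivism and raises receipt of services.

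**The concern.** A youth who accepts post-release support may differ from one who declines it in readiness to change or in wanting treatment. Those traits could also affect later substance use, re-arrest and service use. A balance table on measured variables sees such a trait only as far as a measured variable tracks it, and adjustment has the same limit.

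The SAP stress-tests its missing-data assumption, including a scenario unfavourable to the intervention. It has no counterpart for the assumption of no unmeasured confounding, on which every arm comparison rests. What is at stake is whether a difference between arms, or the lack of one, can be read as an effect of WPC.

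**Working it through.** **1. Does another planned analysis fill the gap?**

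| Planned step | Target | Reaches unmeasured motivation? |
|---|---|---|
| Balance check (Analytic Strategy) | Measured differences | Only through correlated variables |
| Covariate adjustment (Aims 1 to 3) | Measured differences | Only through correlated variables |
| Pattern-mixture imputation (Analytic Strategy) | Missing data | No |
| Principal stratification (Aim 1) | Incarceration during follow-up | No |
| Treatment-received analysis (Analytic Strategy) | Uptake and attrition | No; time in the programme also reflects engagement, so it shares the problem |

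The protocol once planned chart data partly as covariates to control arm differences (adult population, Data Collection). The 10/28/20 amendment dropped the chart abstraction. No propensity method, instrument, negative control or bias analysis appears.

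**2. The plan's own figure.** The Sample Size Estimate gives 160 participants, 10% attrition, two-sided alpha 0.05, 80% power and a detectable difference of 17 points. It gives no SD, so 17 cannot be reproduced independently. Back-solving:

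- Analysed per arm: 160 × 0.9 / 2 = 72.
- SD = 17 / [(1.960 + 0.842) × √(2/72)] = 17 / 0.467 = 36.4 points. With 80 per arm it would be 38.4.
- SE of the difference = 36.4 × √(2/72) = 6.07 points.
- Days: 17% of 30 = 5.1, which agrees with the SAP's 5 days.

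**3. Size of a spurious difference, true effect zero.** Bias = gap × slope × SD. Gap is the arm difference in motivation in SDs; slope is the SD change in use per SD of motivation. Both are assumed.

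| Gap | Slope | Bias (points) | Share of 17 | Bias/SE | False-positive rate |
|---|---|---|---|---|---|
| 0.3 | 0.2 | 0.06 × 36.4 = 2.2 | 13% | 0.36 | 6.5% |
| 0.5 | 0.3 | 0.15 × 36.4 = 5.5 | 32% | 0.90 | 15% |
| 0.8 | 0.4 | 0.32 × 36.4 = 11.6 | 68% | 1.92 | 48% |

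False-positive rate = Φ(b − 1.96) + Φ(−b − 1.96), with b = bias/SE. Because b = gap × slope / √(2/72), the rate does not depend on the back-solved SD. It is the same whichever arm the bias favours.

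**4. How much unmeasured confounding would be enough.** With RR ≈ exp(0.91 × difference/SD) and E-value = RR + √[RR(RR − 1)]:

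- A just-significant difference is 1.96 × 6.07 = 11.9 points, so RR ≈ 1.35 and the E-value is about 2.0.
- The lower limit around an observed 17 points is 17 − 11.9 = 5.1 points, so RR ≈ 1.14 and the E-value is about 1.5.

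**5. Can the balance check see it?** Simulation with 144 analysed, eight measured covariates, adjustment for all eight, zero true effect and 3,000 runs per setting. A run passes if none of the eight differs at the 5% level. Opt-in depends on motivation (log-odds 1 per SD), and motivation lowers use by 6 or 12 points per SD.

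| Setting | Runs passing balance | Adjusted bias (points) | False positives, all runs | False positives, passing runs |
|---|---|---|---|---|
| Arm unrelated to motivation | 65–66% | about 0 | 5–6% | 5–6% |
| Opt-in driven by motivation, covariates unrelated to it | 65–67% | 5.0 to 9.9 | 12–35% | 13–36% |
| Same, one covariate correlated 0.3 with motivation | 46–47% | 4.5 to 9.1 | 11–31% | 12–32% |

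By chance alone, 0.95⁸ = 66% of runs pass. In the second row the check carries no information. In the third it carries some, but adjustment removes under 10% of the bias (for example (9.90 − 9.14)/9.90 = 8%).

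**The case against.** Several points on the other side are sound.

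- **Balance is not the only handling.** A reader might infer that differences are merely inspected. They are not: measured variables that differ enter the models. This stands, but it does not reach unmeasured traits.
- **Some proxies are measured.** A reader might infer that no driver of opting in is captured, or that balance says nothing about them. The documents do not support that. Supportive adults are a network measure, baseline network characteristics are compared, the surveys ask about behavioral health service access, and baseline mental health symptoms are used. The third simulation setting shows that a related covariate makes the check partly informative. The survey instruments are not reproduced, and the SAP text available here starts at Statistical Design and Power, so a motivation item cannot be ruled out. None is named.
- **The arms are not simply joiners against refusers of all support.** Under the SAP, controls received pre-release services. This may narrow the motivation gap; it does not make arm anything but self-selected.
- **Direction.** It is tempting to infer bias towards a false benefit. WPC eligibility requires recent emergency or hospital use plus illness, substance use disorder or homelessness. If those in greatest need opt in more, the bias runs against WPC. The documents settle neither.
- **Magnitude.** Gap and slope are assumed, and the SE is for an unadjusted comparison at one time point while the plan uses adjusted repeated-measures models. The lowest scenario barely departs from 5%.
- **Status.** The protocol (Hypothesis and Specific Aims) calls the study exploratory and observational, and it is a pilot. That tempers severity, but the SAP aims are still worded as impact.

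**Conclusion.** The concern holds in limited form. Arm is self-selected, the only stated examination of selection bias is measured balance, and no analysis in the text available tests or bounds unmeasured confounding. Motivation that is unmeasured, and weakly related to what is measured, could bias the estimate in either direction while balance looks acceptable.

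The illustration gives 2.2 to 11.6 points of bias and a false-positive rate of 6.5% to 48%. It rests on assumed gaps and slopes, 72 analysed per arm and, for the points only, an SD back-solved from the 17-point figure. It shows what is possible and does not estimate the bias in this study.

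A reader might go further and infer that the eventual result will be a false benefit, or that the team will report one. The documents establish neither. This is an inexpensive improvement that should be made; it does not show that the comparison is worthless.

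**What to change.** In the SAP, Analytic Strategy:

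1. Keep the balance check as description and as input to covariate adjustment. Remove its role as the test for selection bias.
2. Add a prespecified quantitative bias analysis for percent of days with marijuana use and for recidivism. Report how strong an unmeasured factor's links to arm and to outcome would have to be to move the adjusted estimate, and its confidence limit nearer the null, to the null. Cover both directions, including how strong a factor could hide a benefit.
3. Show the corresponding links for the measured covariates beside it, for context only. Do not make baseline substance use the sole benchmark: baseline was taken in detention for the initial cohort and is taken two weeks after release for the later one, by which time post-release services may have begun.
4. State that the treatment-received analysis carries the same limitation.
5. Report arm differences as associations whatever the bias analysis shows. A result that withstands it is still not proof of impact in a self-selected comparison.

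The cost is SAP wording and a few lines of code, with no new data or participants. The downside is slightly more analysis and a less favourable wording of the conclusion.
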